Protocol Amendment 1 Final**Table 4** Study groups and treatment foreseen in Part B - Step 2

Treatment name	Vaccine/ Product name	Study Groups									
		30- PLAIN_B2	30- AS01E_B2	30- AS01B_B2	60- PLAIN_B2	60- AS01E_B2	60- AS01B_B2	120- PLAIN_B2	120- AS01E_B2	120- AS01B_B2	Placebo_B2
30 µg RSVPreF3 plain	RSVPreF3 low dose	x									
	NaCl	x									
30 µg RSVPreF3/AS01E	RSVPreF3 low dose		x								
	AS01E		x								
30 µg RSVPreF3/AS01B	RSVPreF3 low dose			x							
	AS01B			x							
60 µg RSVPreF3 plain	RSVPreF3 mid dose				x						
	NaCl				x						
60 µg RSVPreF3/AS01E	RSVPreF3 mid dose					x					
	AS01E					x					
60 µg RSVPreF3/AS01B	RSVPreF3 mid dose						x				
	AS01B						x				
120 µg RSVPreF3 plain	RSVPreF3 high dose							x			
	NaCl							x			
120 µg RSVPreF3/AS01E	RSVPreF3 high dose								x		
	AS01E								x		
120 µg RSVPreF3/AS01B	RSVPreF3 high dose								x		
	AS01B								x		
Placebo	NaCl										x

**CONFIDENTIAL**208851 (RSV OA=ADJ-002)  
Protocol Amendment 1 Final

- **Control:** placebo.
- **Vaccination schedule:** Two vaccine doses administered intramuscularly at Day 1 and Day 61.
- **Blinding:** observer-blind.

The vaccination phases of each study part (Epoch 002) will be observer-blind. A first statistical analysis will be performed on data available up to one month post-Dose 2 (Visit 6, Day 91) (see section 10.12.1 for details on the sequence of analyses). Given that summary safety results may unblind some specific subjects, the persistence phase of Part B (Epoch 003) will be considered as single-blind with subjects remaining blinded up to study end (Visit 8 [Month 14]). The investigators will not be provided with the individual data listings or with the randomization listings until the end of study analysis.

*During the last study visit, blood samples will be collected only from a subset of subjects (N≤460, all subjects in part B1 and subjects who received a selected level of antigen dose and Placebo in part B2). Therefore, the investigators, site and study staff will be partially unblinded at group level, but not at the individual level.*

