**6.4. Replacement of unusable vaccine doses**

In addition to the vaccine doses provided for the planned number of subjects (including over-randomization when applicable), at least 20% additional vaccine doses will be supplied to replace those that are unusable.

The investigator will use SBIR to obtain the replacement vial/syringe number. The replacement numbers will be allocated by dose. The system will ensure, in a blinded manner, that the replacement vial/syringe matches the formulation the subject was assigned to by randomization.

**CONFIDENTIAL**208851 (RSV OA=ADJ-002)  
Protocol Amendment 1 Final**6.5. Contraindications to subsequent vaccination**

The following events constitute absolute contraindications to further administration of the investigational RSV vaccine. If any of these events occur during the study, the subject must not receive additional doses of vaccine but may continue other study procedures at the discretion of the investigator (see Section 9.2.2).

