Paper diary cards will be used by the subjects to capture the details of the unsolicited signs or symptoms. They will be reviewed by the investigator at the subsequent study visits (Day 8, Day 31, Day 68 or Day 91) and then reported as applicable in the AE section of the eCRF.

The subject should be trained on how and when to complete each field of the electronic and paper diary. If a subject is illiterate or unable or not willing to complete the electronic and/or the paper him/herself, he/she may be helped by a designate (refer to the [glossary of terms](#) for the definition of designate).

Subject Diary training should be directed at the individual(s) who will perform the measurements of AEs and who will enter the information into the Subject Diary. If a designate enters information into the Subject Diary, this person's identity must be documented in the subject's source record. Any individual that makes entries into the Subject Diary must receive training on completion of the Subject Diary at the time of the visit when Subject Diary is dispensed. This training must be documented in the subject's source record.

The same individual should complete the Subject eDiary throughout the course of the study. The subject should be trained on how to self-measure local solicited AEs and body temperature. The measurement of solicited local AEs is to be performed using the ruler provided by the site.

**7.3.1. Time period for detecting and recording adverse events, serious adverse events and pregnancies****For Part A and Part B:**

All AEs starting within 30 days following administration of each dose of study vaccine (the day of vaccination and 29 subsequent days) must be recorded into the appropriate section of the eCRF, irrespective of intensity or whether or not they are considered vaccination-related.

All AEs/SAEs leading to withdrawal from the study will be collected and recorded from the time of the first receipt of study vaccine until the subject is discharged from the study.

The time period for collecting and recording SAEs will begin at the first receipt of study vaccine and will end 1 month following administration of the last dose of study vaccine for each subject in Part A and 12 months following administration of the last dose of study vaccine for each subject in Part B. See Section [7.4](#) for instructions on reporting of SAEs.

**CONFIDENTIAL**208851 (RSV OA=ADJ-002)  
Protocol Amendment 1 Final

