**For Part A only:**

The time period for collecting and recording pregnancies will begin at the first receipt of study vaccine and will end 1 month following administration of the last dose of study vaccine. See section [7.4](#) for instructions on reporting of pregnancies.

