**For Part B only:**

The time period for collecting and recording of pIMDs will begin at the first receipt of study vaccine and will end 12 months following administration of the last dose of study vaccine. See Section [7.4](#) for instructions on reporting of pIMDs.

An overview of the protocol-required reporting periods for AEs, SAEs, pregnancies and/or pIMDs is given in

[Table 24](#) for Part A and [Table 25](#) for Part B.

*Refer to Section [5.10](#) for measures for safety follow-up that may be implemented during special circumstances (Amended, 13 May 2020).*

**CONFIDENTIAL**208851 (RSV OA=ADJ-002)  
Protocol Amendment 1 Final**Table 24 Reporting periods for collecting safety information in Part A**

Event	SCR Pre-D1*	Visit 1 Vacc 1	Visit 2	Visit 3	Visit 4 Vacc 2	Visit 5	Visit 6 End of FU for Part A
Solicited local and general AEs			Days 1-7			Days 61-67	
Unsolicited AEs			Days 1-30			Days 61-90	
AEs/SAEs leading to withdrawal from the study					Days 1-91		
SAEs					Days 1-91		
SAEs related to study participation or concurrent GSK medication/vaccine					Pre-Day 1* - Day 91		
Pregnancies					Days 1-91		
Intercurrent medical conditions					Days 1-91		

\* i.e., consent obtained.

Pre-D1: Pre-vaccination Day 1; FU: Follow-up; Vacc: Vaccination; SCR: Screening Visit

**CONFIDENTIAL**208851 (RSV OA=ADJ-002)  
Protocol Amendment 1 Final**Table 25 Reporting periods for collecting safety information in Part B**

Event	SCR Pre-D1*	Visit 1 Vacc 1	Visit 2	Visit 3	Visit 4	Visit 5	Visit 6	Visit 7	Visit 8 Study Conclusion
Solicited local and general AEs			Days 1-7			Days 61-67			
Unsolicited AEs			Days 1-30			Days 61-90			
AEs/SAEs leading to withdrawal from the study					Day 1 - Month 14				
SAEs					Day 1 - Month 14				
SAEs related to study participation or concurrent GSK medication/vaccine					Pre-Day 1* - Month 14				
plMDs					Day 1 - Month 14				
Intercurrent medical conditions					Day 1 - Month 14				

\* i.e., consent obtained.

Pre-D1: Pre-vaccination Day 1; Vacc: Vaccination

SCR: Screening Visit

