**7.10.3.2. Process of suspension of vaccination and/ or study modification**

In the event that a safety signal is observed, the sponsor might decide to cancel vaccination of all groups or selected groups.

**CONFIDENTIAL**208851 (RSV OA=ADJ-002)  
Protocol Amendment 1 Final

In this case, for impacted groups:

- Subjects who were already vaccinated will not receive the second study vaccine dose (if not yet administered) and continue all other visits as planned.
- Subjects who signed an informed consent but did not receive any study vaccine will be informed that their study participation will be stopped.

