### 10.1. Primary endpoints

#### For Part A and Part B:

- Occurrence of AEs from first vaccination up to 30 days after the second vaccination (Day 91):
  - Occurrence of each solicited local and general AE during a 7-day follow-up period (i.e., on the day of vaccination and 6 subsequent days) after each vaccination.
  - Occurrence of any unsolicited AE during a 30-day follow up period (i.e., on the day of vaccination and 29 subsequent days) after each vaccination.
  - Occurrence of any hematological (erythrocytes, WBC and differential count, platelets count and hemoglobin level) and biochemical (ALT, AST, creatinine, BUN and uric acid) laboratory abnormalities at Days 1, 8, 61 and 68.
  - Occurrence of all Grade 3 non-serious AEs (solicited and unsolicited) during the 30-day follow-up period after each vaccination.
  - Occurrence of SAEs from Dose 1 up to 30 days after the second vaccine dose (Day 91).

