**For Part B only:**

- Occurrence of RSV-associated RTI (as measured by qRT-PCR in nasal/throat swab samples collected during the assessment visit for potential RSV-RTI) during the RSV seasons, up to the end of follow-up.
- Occurrence of SAEs from Dose 1 up to the end of follow-up.
- Occurrence of pIMDs from Dose 1 up to the end of follow-up.

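### Section 7.3.1, read literally, ends SAE, pregnancy and pIMD collection early for subjects who receive only Dose 1, in conflict with Tables 24/25 and the SAE and pIMD endpoints

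*Protocol*

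**What the plan says.** The schedule in Section 3 is "Two vaccine doses administered intramuscularly at Day 1 and Day 61".

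Section 7.3.1 sets the end of collection by the last dose:
- SAEs: collection "will end 1 month following administration of the last dose of study vaccine for each subject in Part A and 12 months following administration"; the second period is for Part B.
- Pregnancies, Part A: collection "will end 1 month following administration of the last dose of study vaccine".
- pIMDs, Part B: collection "will end 12 months following administration of the last dose of study vaccine". The risk table in Section 1.3.1 repeats this 12-month rule.

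Tables 24 and 25, which the same section offers as the overview of these periods, give Days 1-91 for SAEs and pregnancies in Part A, and Day 1 to Month 14 for SAEs and pIMDs in Part B. Neither table has a condition on doses received.

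The protocol foresees subjects with one dose who stay in the study. Section 7.10.3.2, on a group cancelled for a safety signal, says: "Subjects who were already vaccinated will not receive the second study vaccine dose (if not yet administered) and continue all other visits as planned". Section 6.5, on individual contraindications, says that "the subject must not receive additional doses of vaccine but may continue other study procedures at the discretion of the investigator". Section 9.2.2 also separates withdrawal from vaccine from withdrawal from the study.

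The primary SAE endpoint in Section 10.1 prints Day 91 as its end. The Part B secondary endpoint in Section 10.2 is "Occurrence of SAEs from Dose 1 up to the end of follow-up", with a parallel one for pIMDs; Section 2.2 gives the end of follow-up as Month 14, Visit 8.

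**The concern.** The SAE sentence is worded per subject, so its natural literal sense is the last dose that the subject actually received. On that sense a one-dose subject's window closes before the window in Tables 24/25 and before the end of the endpoint that the data must serve. No sentence says which rule prevails. The ambiguity also reaches the reporting duty, because Section 7.4.1 ties prompt reporting of SAEs, pregnancies and pIMDs to the period set in Section 7.3.

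The subjects affected are not a random subset. They include those stopped for a related SAE, a pregnancy, a pIMD or a laboratory abnormality, and any group cancelled for a signal. Under Section 10.6 every vaccinated subject is in the denominator and a subject without a report counts as having no event. Section 10.8 summarises SAEs and pIMDs as percentages of subjects. A shorter window would therefore lower the observed rate in exactly the subjects or groups stopped for safety.

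**Working it through.** **Inputs.** Dose 1 on Day 1 and Dose 2 on Day 61, that is Month 2 (Section 3). Window after the last dose: 1 month, taken as 30 days, in Part A; 12 months in Part B (Section 7.3.1). Table periods: Day 91 and Month 14 (Tables 24/25).

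**Formula.** End of collection = time of last dose + window.

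| | Two doses, 7.3.1 text | One dose, 7.3.1 text | Tables 24/25 |
|---|---|---|---|
| Part A | Day 61 + 30 = Day 91 | Day 1 + 30 = Day 31 | Day 91 |
| Part B | Month 2 + 12 = Month 14 | Month 0 + 12 = Month 12 | Month 14 |

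For two doses the text reproduces the tables. For one dose it does not.

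**Loss under the literal text.**
- Part A: 91 - 31 = 60 days; 60/91 = 66% of the period. Visits 4, 5 and 6 (Days 61, 68 and 91) all fall after the window.
- Part B: 14 - 12 = 2 months; 2/14 = 14%. Only Visit 8 falls after the window.

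**Endpoints reached.**
- Part A primary SAE endpoint (Day 91): cut, since Day 31 is earlier.
- Part B primary SAE and pIMD endpoints (Day 91): not cut, since Month 12 is later.
- Part B secondary SAE and pIMD endpoints (Month 14): cut by 2 months.
- Pregnancy is not an endpoint, so there the conflict is with Tables 6 and 24. It is still concrete: Section 5.7.1 requires a test at Visit 4 (Day 61), and a positive result bars Dose 2, yet the literal window would have closed at about Day 31.

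**What the loss could mean for one group (illustration only).** The protocol gives no SAE rate. Assume 0.2% to 1% per subject-month, independent across months. The chance of at least one SAE in the 2 lost months is 1 - (1 - r)^(2n):
- Part A group, n = 12, 24 subject-months: 1 - 0.998^24 = 5% to 1 - 0.99^24 = 21%.
- Part B group, n = 100, 200 subject-months: 1 - 0.998^200 = 33% to 1 - 0.99^200 = 87%.

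**The case against.** The strongest reply is that the protocol, read as a whole, already calls for full collection.
- The objectives (Sections 2.1 and 2.2) use last dose for the scheduled second dose and gloss one month after it as Day 91, Visit 6. On that sense Section 7.3.1 agrees with the tables.
- Tables 6 and 7 schedule SAE recording at every visit from Visit 1 with no dose condition; Table 6 does the same for pregnancies and Table 7 for pIMDs.
- Section 7.3.2 defines a post-study event by Tables 24/25, so an SAE on Day 50 in a one-dose Part A subject is inside the reporting period.
- Section 7.10.3.2 keeps cancelled groups in all remaining visits, and Appendix D continues all other safety and immunology procedures when a holding rule is met.
- Section 5.10 collects SAEs and pIMDs at Visit 8 without regard to doses received.

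All of this stands. A reader might infer from Section 7.3.1 that an arm halted for safety simply stops SAE collection at about Day 31; the passages above do not support that as the settled rule. A reader might also infer that Visits 5 to 8 cannot be timed without Dose 2. They can: Table 8 times them from Visit 4, which has its own interval from Visit 1 and its own non-vaccine procedures.

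What remains is that the SAE sentence speaks of each subject, the pregnancy and pIMD sentences follow the same pattern, and nothing ranks them against the tables. The existing safeguards are partial. Events leading to study withdrawal, and SAEs related to study participation or to a concurrent product of the sponsor, are collected to discharge. Vaccine-related SAEs after the study are notified only if the investigator learns of them.

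**Conclusion.** The point holds as an internal contradiction in wording. Taken literally, Section 7.3.1 would remove about 60 of 91 days of SAE and pregnancy collection for a one-dose subject in Part A, and 2 of 14 months of SAE and pIMD collection in Part B. It would cut the Part A primary SAE endpoint and the Part B secondary SAE and pIMD endpoints, and leave the Part B primary endpoints intact. Any bias would be downward in subjects or groups stopped after one dose.

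This rests on last dose meaning the dose actually received, and on sites following that sentence over the visit tables. Most other passages point the other way, so the loss is a risk and not an expected outcome. The number of subjects affected cannot be derived, since the protocol gives no rate of missed second doses; a whole cancelled group would be 12 subjects in Part A or about 100 in Part B.

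**What to change.** Reconcile the SAE, pregnancy and pIMD sentences in Section 7.3.1, and the pIMD statement in Section 1.3.1, with Tables 24/25. State that collection starts at the first dose and runs to Day 91 (Visit 6) in Part A and Month 14 (Visit 8) in Part B for every vaccinated subject, regardless of the number of doses received. Naming the visit beside the nominal time is useful: with the Dose 2 interval of 55 to 80 days in Part A (Table 8), Dose 2 plus 30 days falls anywhere from Day 1 + 55 + 30 = 86 to Day 1 + 80 + 30 = 111.

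No change is needed to Table 8 or to the Part B primary pIMD endpoint.

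The cost is four sentences and no new visits, samples or forms, because the visit tables already schedule the collection. Section 5.10 treats Visit 8 as the one scheduled visit remaining at Amendment 1, so the Month 12 to 14 gap in Part B is the part that wording can still affect. For Part A, the study report should confirm that one-dose subjects, if any, were followed to Day 91.

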**For Part A only:**

The time period for collecting and recording pregnancies will begin at the first receipt of study vaccine and will end 1 month following administration of the last dose of study vaccine. See section [7.4](#) for instructions on reporting of pregnancies.

**For Part B only:**

The time period for collecting and recording of pIMDs will begin at the first receipt of study vaccine and will end 12 months following administration of the last dose of study vaccine. See Section [7.4](#) for instructions on reporting of pIMDs.

An overview of the protocol-required reporting periods for AEs, SAEs, pregnancies and/or pIMDs is given in

[Table 24](#) for Part A and [Table 25](#) for Part B.

*Refer to Section [5.10](#) for measures for safety follow-up that may be implemented during special circumstances (Amended, 13 May 2020).*

**CONFIDENTIAL**208851 (RSV OA=ADJ-002)  
Protocol Amendment 1 Final**Table 24 Reporting periods for collecting safety information in Part A**

Event	SCR Pre-D1*	Visit 1 Vacc 1	Visit 2	Visit 3	Visit 4 Vacc 2	Visit 5	Visit 6 End of FU for Part A
Solicited local and general AEs			Days 1-7			Days 61-67	
Unsolicited AEs			Days 1-30			Days 61-90	
AEs/SAEs leading to withdrawal from the study					Days 1-91		
SAEs					Days 1-91		
SAEs related to study participation or concurrent GSK medication/vaccine					Pre-Day 1* - Day 91		
Pregnancies					Days 1-91		
Intercurrent medical conditions					Days 1-91		

\* i.e., consent obtained.

Pre-D1: Pre-vaccination Day 1; FU: Follow-up; Vacc: Vaccination; SCR: Screening Visit

**CONFIDENTIAL**208851 (RSV OA=ADJ-002)  
Protocol Amendment 1 Final**Table 25 Reporting periods for collecting safety information in Part B**

Event	SCR Pre-D1*	Visit 1 Vacc 1	Visit 2	Visit 3	Visit 4	Visit 5	Visit 6	Visit 7	Visit 8 Study Conclusion
Solicited local and general AEs			Days 1-7			Days 61-67			
Unsolicited AEs			Days 1-30			Days 61-90			
AEs/SAEs leading to withdrawal from the study					Day 1 - Month 14				
SAEs					Day 1 - Month 14				
SAEs related to study participation or concurrent GSK medication/vaccine					Pre-Day 1* - Month 14				
plMDs					Day 1 - Month 14				
Intercurrent medical conditions					Day 1 - Month 14				

\* i.e., consent obtained.

Pre-D1: Pre-vaccination Day 1; Vacc: Vaccination

SCR: Screening Visit

### 7.3.2. Post-Study adverse events and serious adverse events

A post-study AE/SAE is defined as any event that occurs outside of the AE/SAE reporting period defined in

[Table 24](#) for Part A and [Table 25](#) for Part B. Investigators are not obligated to actively seek AEs or SAEs in former study participants. However, if the investigator learns of any SAE at any time after a subject has been discharged from the study, and he/she considers the event reasonably related to the study vaccine, the investigator will promptly notify the Study Contact for Reporting SAEs.

**CONFIDENTIAL**208851 (RSV OA=ADJ-002)  
Protocol Amendment 1 Final**7.3.3. Evaluation of adverse events and serious adverse events****7.3.3.1. Active questioning to detect adverse events and serious adverse events**

As a consistent method of collecting AEs, the subject should be asked a non-leading question such as:

*'Have you felt different in any way since receiving the vaccine or since the previous visit?'*

When an AE/SAE occurs, it is the responsibility of the investigator to review all documentation (e.g. hospital progress notes, laboratory and diagnostics reports) relative to the event. The investigator will then record all relevant information regarding an AE/SAE in the eCRF. The investigator is not allowed to send photocopies of the subject's medical records to GSK Biologicals instead of appropriately completing the eCRF. However, there may be instances when copies of medical records for certain cases are requested by GSK Biologicals. In this instance, all subject identifiers will be blinded on the copies of the medical records prior to submission to GSK Biologicals.

The investigator will attempt to establish a diagnosis pertaining to the event based on signs, symptoms, and/or other clinical information. In such cases, the diagnosis should be documented as the AE/SAE and not the individual signs/symptoms.

**7.3.3.2. Assessment of adverse events****7.3.3.2.1. Assessment of intensity**

The intensity of the following solicited AEs will be assessed as described:

**CONFIDENTIAL**208851 (RSV OA=ADJ-002)  
Protocol Amendment 1 Final**Table 26 Intensity scales for solicited symptoms in adults**

Adverse Event	Intensity grade	Parameter
Pain at injection site	0	None
	1	Mild: Any pain neither interfering with nor preventing normal every day activities.
	2	Moderate: Painful when limb is moved and interferes with every day activities.
	3	Severe: Significant pain at rest. Prevents normal every day activities.
Redness at injection site		Record greatest surface diameter in mm
Swelling at injection site		Record greatest surface diameter in mm
Fever*		Record temperature in °C/°F
Headache	0	Normal
	1	Mild: Headache that is easily tolerated
	2	Moderate: Headache that interferes with normal activity
	3	Severe: Headache that prevents normal activity
Fatigue	0	Normal
	1	Mild: Fatigue that is easily tolerated
	2	Moderate: Fatigue that interferes with normal activity
	3	Severe: Fatigue that prevents normal activity
Gastrointestinal symptoms (nausea, vomiting, diarrhoea and/or abdominal pain)	0	Normal
	1	Mild: Gastrointestinal symptoms that are easily tolerated
	2	Moderate: Gastrointestinal symptoms that interfere with normal activity
	3	Severe: Gastrointestinal symptoms that prevent normal activity
Arthralgia	0	Normal
	1	Mild: Arthralgia that is easily tolerated
	2	Moderate: Arthralgia that interferes with normal activity
	3	Severe: Arthralgia that prevents normal activity
Myalgia	0	Normal
	1	Mild: Myalgia that is easily tolerated
	2	Moderate: Myalgia that interferes with normal activity
	3	Severe: Myalgia that prevents normal activity
Shivering	0	Normal
	1	Mild: Shivering that is easily tolerated
	2	Moderate: Shivering that interferes with normal activity
	3	Severe: Shivering that prevents normal activity

\*Fever is defined as temperature  $\geq 38.0^{\circ}\text{C}$  /  $100.4^{\circ}\text{F}$  (regardless of the location of measurement). The preferred location for measuring temperature in this study will be the oral cavity.

The maximum intensity of local injection site redness/swelling and fever will be scored at GSK Biologicals as follows:

	Redness/swelling	Fever
0:	$\leq 20$ mm	$< 38.0^{\circ}\text{C}$ ( $100.4^{\circ}\text{F}$ )
1:	$> 20 - \leq 50$ mm	$\geq 38.0^{\circ}\text{C}$ ( $100.4^{\circ}\text{F}$ ) - $\leq 38.5^{\circ}\text{C}$ ( $101.3^{\circ}\text{F}$ )
2:	$> 50 - \leq 100$ mm	$> 38.5^{\circ}\text{C}$ ( $101.3^{\circ}\text{F}$ ) - $\leq 39.0^{\circ}\text{C}$ ( $102.2^{\circ}\text{F}$ )
3:	$> 100$ mm	$> 39.0^{\circ}\text{C}$ ( $102.2^{\circ}\text{F}$ )

The investigator will assess the maximum intensity that occurred over the duration of the event for all unsolicited AEs (including SAEs) recorded during the study. The assessment will be based on the investigator's clinical judgement.

**CONFIDENTIAL**208851 (RSV OA=ADJ-002)  
Protocol Amendment 1 Final

The intensity should be assigned to one of the following categories:

- 1 (mild) = An AE which is easily tolerated by the subject, causing minimal discomfort and not interfering with everyday activities.
- 2 (moderate) = An AE which is sufficiently discomforting to interfere with normal everyday activities.
- 3 (severe) = An AE which prevents normal, everyday activities  
 In adults, such an AE would, for example, prevent attendance at work/school and would necessitate the administration of corrective therapy.)

An AE that is assessed as Grade 3 (severe) should not be confused with an SAE. Grade 3 is a category used for rating the intensity of an event; and both AEs and SAEs can be assessed as Grade 3. An event is defined as ‘serious’ when it meets one of the pre-defined outcomes as described in Section [7.1.2](#).

